6.2. Statistical analysis of clinical outcomes

General principles

The statistical analyses will be performed by the INSERM CIC 1415 unit and supervised by [name]. SAS 9.4 and R 3.3 (or further versions) softwares will be used. A detailed analysis plan will be *a priori* defined. Later modifications must occur before unblinding the database. The statistical analysis will be conducted on the per-protocol and intention to treat (ITT) populations as recommended for non inferiority trials. A statistical report will be written in agreement with the standards as specified in the CONSORT Statement and its extension for non pharmacological interventions and for non inferiority trials (<http://www.consort-statement.org/>)

Baseline characteristics

Baseline characteristics will be reported per group using descriptive statistics. No statistical test will be performed.

Groups to be compared

The ITT principle will be applied. Nevertheless, patients who would withdrew consent to study participation will be discarded, as required by the French legislation.

Because patients are ICU patients, it is expected to have no lost-to-follow-up patient. We moreover plan to collect the place of birth, such that we will be able to collect the vital status asking to the city halls. If there are several lost-to follow-up patients, we will use multiple imputation.

The per protocol population will be defined during the blind review.

Statistical analysis of the primary outcome

The between-group difference (experimental group minus usual care group) in rates of day-28 mortality will be estimated based on the 2-sided 95% Confidence Interval (CI). The upper boundary of the 95% CI will be compared with the non inferiority margin of 5%. If non-inferiority is demonstrated, the upper bound of the 95%CI will be compared to 0: if it is lower than 0, then a superiority conclusion will be drawn.(68)

As a sensitivity analysis, we will perform a multivariate logistic regression, to estimate the odds ratio adjusted on the stratification variables.(69)

Statistical analysis of secondary clinical outcomes

- Day-90 mortality: the between-group difference in rates of day-90 mortality will be estimated based on the 2-sided 95% CI.
- Number of patients who underwent IAC insertion, in both groups.

No statistical test will be performed for this outcome, which would be nonsense.

In the usual care group, the proportion of patients who underwent IAC is a measure of adherence. In the experimental group, the proportion of patients who underwent IAC is of relevance as it reflects the limits of the non-invasive approach.

- The effect of intervention on changes over time of the SOFA score, the blood haemoglobin level, haematocrit, mean daily blood volume drawn for lab testing, mean daily amount of intravenous fluids given for rapid vascular volume expansion, mean daily fluid balance, daily maximum pain and associated 95%CI will be estimated using mixed linear models, after data transformation if necessary.
- Duration of mechanical ventilation will be analysed using a competing risk approach, with death as competing risk.
- The effect of intervention on proportion of patients treated by renal-replacement therapy or by vasopressor, proportions of patients with arterial and central venous catheter-related infections or bloodstream infections and associated 95%CI will be estimated using the competing risk approach, with death as competing risk.
- The effect of intervention on number of blood cultures performed, number of attempts at arterial puncture, number of red blood cell packs transfused, number of arterial and central venous catheter insertion and associated 95%CI will be estimated using negative binomial models with duration of ICU stays as offset variable.
- Two-sided 95% CIs of median differences of free-days (Ventilator-free days, renal replacement therapy-free days, vasopressor therapy-free days) will be estimated.
- Duration of ICU and hospital stay: 2-sided 95% CIs of median differences will be estimated.

- The effect of intervention on ICU and hospital mortality and 95% CI will be estimated using competing-risk model with ICU and hospital discharge alive as competing events with death during the stay.

6.3. Statistical analysis of medico-economic outcomes

General principles

Cost-effectiveness analyses will be performed by the Medico-Economic Evaluation Unit of Tours University Hospital and supervised by [name]. They will be based on the effectiveness results obtained by the INSERM CIC 1415 and follow standard recommendations for health-economic analyses (HAS).

Medico-economic objectives

Medico-economic evaluation comprises three secondary objectives:

- To assess the impact of the non-invasive strategy on the direct hospital medical costs of care
- To determine the efficiency of the non-invasive strategy when compared to the recommended invasive strategy (ICER: 'Cost/Life day gained at 28 days')
- To evaluate the budget impact of the generalization of the non-invasive strategy (in case of demonstrated non inferiority) in France from the viewpoint of the French health system on a 5 years' time frame

Therefore, medico-economic criteria are:

- Nurse and physician time (min) spent for arterial and venous puncture for lab tests, arterial catheter insertion and set up of monitor, blood drawings from arterial catheter or other vascular line through ICU stay (in a random sample representing 10% of the total number of included patients)
- Incremental Cost-Effectiveness Ratio (ICER): «Cost/Life day gained at 28 days», from the health system viewpoint, between the non invasive strategy and the recommended invasive strategy: $(\text{Costs}_{\text{NIBP}} - \text{Costs}_{\text{IAC}}) / (\text{Life expectancy at D28}_{\text{NIBP}} - \text{Life expectancy at D28}_{\text{IAC}})$
- Budget impact analysis (BIA) of the generalization of the non-invasive strategy (in case of demonstrated non inferiority) in France from the viewpoint of the French health system on a 5 years' time frame

Cost study and cost-effectiveness analysis

The cost-effectiveness study will last 28 days and will take into account two viewpoints (Health insurance and hospital). The ITT principle will be applied.

Only the direct medical costs related to the hospitalization will be retained. Indeed, patients will be treated almost exclusively in hospitals during this time horizon. The direct link between one hospitalization and the strategy will be checked. Consumed resources will be collected during and at the end of the study:

- 1) A microcosting will be performed to count and time resources used in ICU for some specific steps from randomisation through day 28:
 - a. preparation and insertion of an IAC and set up of monitor
 - b. NIBP measurement by oscillometry
 - c. arterial and venous blood sampling
 - d. peripheral pulse oximetry readings (SpO_2)
 - e. transfusion (number of packed red blood cell transfused)
 - f. dressing changes

Staff resources (physician, nurse...) will be reported and timed separately. The equipment used for these steps will also be collected. The microcosting will be carried out in each centre on a sample of randomly selected patients (10%) and data will be collected in the Case report Form (CRF). Data from microcosting will allow us to present the results from the health institutions viewpoint.

- 2) A query of the hospital databases (FNHDD) will take place at the end of the study to collect actual billing data for health insurance (DRG and supplements). This step will include all patients stay data from randomisation to day 28. The coding practices for DRG will be evaluated to take into account the heterogeneity of each centre. A specific attention will be paid to comorbidity (associated diagnosis) that can affect the grouping function and possibly modify the DRG. The hospitalization data, and particularly the activity data, will be analysed to compare patterns of patient's care and comorbidity. Because of the continuous evolution of the DRG classification, hospital stays will be reallocated in the latest classification to keep consistency of data. Data from hospital databases will be used to present results from the health insurance viewpoint.

The valuation of consumed resources during hospitalization will be done from the FNHDD, the national health costs scale (ENCC), public wage grid and public prices of resources measured by microcosting.

Discounting will be applied to costs from the ENCC data to bring them forward to the current year.

Nurse and physician time (min) spent for arterial puncture, arterial catheter insertion and set up of monitor will be compared between both groups.

The overall costs will be computed by multiplying the numbered resources (from the economic data collection) by their respective costs (from the medical service valuation).

Firstly, economic data will be used to describe the population (descriptive analysis). A comparison of economic data (DRG and new hospitalisations) from both groups will be carried out.

The ICER «Cost/ Life day gained at 28 days» was chosen to rely on the primary judgment criterion. As usual, it will be evaluated on the same timeframe for costs and effectiveness. It will be computed and presented in a cost-effectiveness plan.

A cost-effectiveness acceptability curve will be drawn from a bootstrap simulation to show the probability that the studied strategy is cost-effective for a ceiling ratio. This ratio is determined as the maximum cost that decision makers are willing to pay for one gained life day at 28 days.

According to the “HAS” guide for economic evaluation, sensitivity analysis will be led to evaluate the sturdiness of the results. It will allow us to take into account the uncertainty of surrounding various parameters of the evaluation. The variables challenged in the sensitivity analysis will be costs and results (especially the nursing and physician time and the equipment used).

The uncertainty of the ICER will be assessed using one-way deterministic sensitivity analyses (use of Tornado diagram to present the results).

Budget Impact Analysis

Only if the non-inferiority of the non-invasive strategy is demonstrated, the BIA will determine the financial impact (potential savings) of the wider use of the non-invasive strategy for all eligible patients in France. The budget impact will be analysed from the viewpoint of the health system (Hospital and Health Insurance) over a 5-years' time frame. No discounting will be applied to the BIA data, in accordance with HAS recommendations.

The BIA will consist in multiplying the average annual cost per patient over 5 years by the number of eligible patients, taking into account a penetration rate. We will estimate the financial impact of the non-invasive strategy considering the current and future target populations (such data will be collected from the literature and expert opinions).

Excel®, SAS 9.4, STATA 15 and TreeAge Pro® softwares will be used for all medico-economic analyses.

7. Feasibility

The feasibility of the proposed study is based on (i) the ability of involved ICUs and investigators to recruit patients, (ii) their expertise in the field of shock resuscitation, (iii) their experience regarding inclusion in and conduct of interventional studies in the field of resuscitation, (iv) logistical support provided by the CRICS group and (v) the involvement of the CIC and the UEME-CHU Tours for the methodological, statistical expertise, and database management.

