- Renal replacement therapy-free days from Day 1 to Day 28 (for this purpose days without renal replacement therapy from Day 1 to Day 28 for survivors at Day 28, and from Day 1 to the date of death for patients dying before Day 28, will be taken into account)
- Proportion of patients treated by vasopressor between Day 1 and Day 28
- Vasopressor therapy-free days from Day 1 to Day 28 (for this purpose days without vasopressor therapy from Day 1 to Day 28 for survivors at Day 28, and from Day 1 to the date of death for patients dying before Day 28, will be taken into account)
- Mean daily blood volume drawn for lab testing during ICU stay
- Number of blood cultures performed during ICU stay
- Number of attempts at arterial puncture during ICU stay
- Evolution of blood haemoglobin level from Day 1 to Day 28
- Evolution of haematocrit from Day 1 to Day 28
- Number of red blood cell packs transfused from Day 1 to Day 28
- Number of transcutaneous arterial and venous puncture for lab tests, arterial catheter insertion and set up of monitor, blood drawing from the arterial catheter or other vascular line through ICU stay and time (min) spent by nurses and physicians (min) on these tasks during the first three days of the

ICU stay (in a random sample representing 10% of the total number of included patients).

- Number of arterial and central venous catheter insertion during ICU stay
- Numbers of arterial and central venous catheter-related infections during ICU stay, expressed as the incidence of new cases per 1000 catheter-days, including local and catheter-related bloodstream infections as consensually defined.(58,59)
- Numbers of local infections of arterial and central venous during ICU stay (number of new cases per 1000 catheter-days).
- Numbers of arterial and central venous catheter-related bloodstream infections during ICU stay, (number of new cases per 1000 catheter-days).
- Number of bloodstream infections during ICU stay, catheter-related or not
- Duration of ICU stay
- Duration of hospital stay
- ICU mortality
- Hospital mortality
- Day-90 mortality

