3.1. Differences between the usual care and the non-invasive care strategies

Description of blood pressure monitoring among randomisation group

In the “usual care” group, BP will be monitored through the arterial line sensor connected to the usual monitoring device (fluid-filled system). Site of IAC insertion, insertion technique, skin antisepsis and catheter care will be at the discretion of the attending physician, according to local guidelines. Non-invasive BP monitoring is not allowed, except when IAC is considered futile (as defined above) and during IAC insertion or replacement.

In the “non-invasive” group, automated oscillometric monitor will be used to monitor BP. ***The size of the cuff will be adapted according of the arm circumference and manufacturer recommendations.*** The dedicated indicator will be placed at the level of the artery. If deemed appropriate according to clinical context, the cuff may be placed at the lower limb.(30)

In both groups, alarm thresholds and interval of BP measurements will be left at the discretion of the attending physician.

Blood sampling technique

In the “usual care” group, blood samples for lab tests will be drawn from the IAC, as many times as

necessary. Blood-drawing through the central venous catheter is forbidden, excepted for ScvO₂ measurements.

In the “non-invasive” group, blood-drawing through the central venous catheter is recommended for usual lab tests. To avoid interruption or bolus on specific continuous therapeutics, we strongly recommend infusing vasopressor agents in a dedicated line of the central venous catheter that should not be the line used for sampling. Regarding the monitoring of ventilation parameters and of the lactate blood level, we encourage the attending intensivists and investigators to rely on SpO₂ (60,61) to assess oxygenation, and on predicted pH, PaCO₂, and lactate derived from central venous blood analysis.(47) For this purpose, formula to derive estimates of arterial blood parameters and abacuses giving probabilities of true arterial values below or above given thresholds for each predicted value will be provided to the sites (APPENDIX 2).

Arterial blood gas parameters

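### The stated between-group comparison of staff time covers three of the five tasks in the protocol's own criterion, omitting venous punctures and all blood draws from lines

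*Protocol*

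**What the plan says.** Section 6.3 of the Protocol (Medico-economic objectives) lists nurse and physician time as a medico-economic criterion, over these tasks: "arterial and venous puncture for lab tests, arterial catheter insertion and set up of monitor, blood drawings from arterial catheter or other vascular line". It is to be measured in a random 10% of patients. Section 2.3 sets the same tasks as a secondary outcome, beginning "Number of transcutaneous arterial and venous puncture for lab tests, arterial catheter insertion and set up of monitor", and adds line draws and the "time (min) spent by nurses and physicians (min) on these tasks during the first three days". The schedule in section 4.6 repeats the list in its rows for counts and for microcosting.

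Later in section 6.3, under Cost study and cost-effectiveness analysis, the comparison is specified as: "Nurse and physician time (min) spent for arterial puncture, arterial catheter insertion and set up of monitor will be compared between both groups". That list contains neither venous puncture nor draws from any line.

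The same subsection makes "arterial and venous blood sampling" a microcosted step and has staff time recorded separately by type of staff. Section 3.1 sets the sampling routes. Usual-care samples come from the arterial catheter, and central venous draws are ruled out there except for ScvO2. In the non-invasive arm, "blood-drawing through the central venous catheter is recommended for usual lab tests".

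**The concern.** A criterion and its analysis should cover the same quantity. Here the analysis sentence is narrower than the criterion, and the missing tasks are ones on which the two strategies are designed to differ. A result reported as staff time by strategy would leave out most routine laboratory sampling in both arms, while keeping catheter insertion and monitor set-up, which fall mainly on usual care.

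Staff time matters to the protocol's argument. Section 1.3 uses insertion time as part of the cost rationale, and section 6.3 singles out nursing and physician time for sensitivity analysis. A reader given only the three-task comparison could not tell whether time saved on insertion is offset, or added to, by differences in sampling work.

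**Working it through.** The plan states no numerical target for staff time, so there is no figure to reproduce. The check is a comparison of task lists, followed by an illustration of scale.

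**Task lists side by side**

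| Task | Criterion (2.3, 4.6, 6.3 objectives) | Comparison (6.3 cost study) | Where it falls, from sections 3 and 3.1 |
|---|---|---|---|
| Arterial puncture | Yes | Yes | Permitted as often as indicated in the non-invasive arm |
| Arterial catheter insertion | Yes | Yes | Mainly usual care; in the non-invasive arm only if safety criteria are met |
| Monitor set-up | Yes | Yes | As for insertion |
| Venous puncture for laboratory tests | Yes | No | Not stated by arm |
| Draws from a line | Yes | No | Arterial catheter in usual care; central venous catheter in the non-invasive arm |

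The comparison keeps three of five elements. The line-draw element is the main sampling route in each arm.

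**Does another section supply the missing comparison?** No. Section 6.2 deals with clinical outcomes and does not mention staff time. The rest of section 6.3 covers costs, the cost-effectiveness ratio and the budget impact. The SAP analyses some counts (arterial puncture attempts, draws from the venous catheter) but has no staff-time analysis.

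**Time window.** Four statements differ:
- Section 2.3: time over the first three days of the ICU stay.
- Section 4.6: the microcosting row is marked for days 1 to 3 but worded as running through the ICU stay.
- Section 6.3, criterion: "blood drawings from arterial catheter or other vascular line through ICU stay".
- Section 6.3, microcosting: randomisation through day 28.

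**Scale, as illustration only.** Write the full difference (non-invasive minus usual care) as

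full difference = three-task difference + omitted difference.

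The one time given in the documents is in section 1.3: 20 min of physician time + 20 min of nurse time = 40 staff-minutes per insertion. Time per draw and the difference in number of draws are not given. Assume equal time m per draw or puncture in both arms, a net difference of one per day in either direction, and three days. The omitted difference is then ± 3 × m:

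- m = 3 min: ± 9 min, and 9/40 = 22.5% of one insertion
- m = 5 min: ± 15 min, and 15/40 = 37.5%
- m = 10 min: ± 30 min, and 30/40 = 75%

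Equivalently, one insertion is matched by a net difference of 40/10 = 4 to 40/3 ≈ 13 draws. The omitted part could be material, but its sign is open.

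**Sample.** 10% of 1010 is 101 patients, about 50 per arm and about 101/11 ≈ 9 per centre. Widening the task list does not change this.

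**The case against.** The strongest reply is that the short list is loose drafting. The sentence does not withdraw the full criterion, which is stated three times elsewhere, and blood sampling is still timed. That may well be so, but it is the only sentence saying what will be compared, so an analyst following it would report the shorter list. If it is a slip, repeating the full list corrects it.

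Two stronger readings are tempting, and the documents support neither.

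First, a reader might infer that the comparison is biased in favour of the non-invasive arm, because insertion is counted and the sampling that replaces catheter draws is not. But draws from the arterial catheter are dropped too, and arterial punctures, which the non-invasive arm may need more often, are kept. The synopsis says that a catheter increases the number of samples ordered, so leaving out draws could equally hide a saving in the non-invasive arm. Section 3.1 gives one draw procedure for both catheter types, differing in discard volume (3 mL against 5 mL), so it gives no basis for assuming that a venous draw takes longer.

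Second, a reader might infer that the claimed savings are wrong. Overall costs are built from the microcosted resources, which include arterial and venous sampling. Nothing shows that this work is left out of overall costs, the cost-effectiveness ratio or the budget impact.

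It is also fair to say that cuff measurement and dressing changes, although microcosted, are not in the staff-time criterion. Their absence from the comparison is not an inconsistency.

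**Conclusion.** The point stands as a mismatch between a secondary medico-economic criterion and its stated analysis. Followed as written, the comparison estimates time on three of five defined tasks and omits the main sampling work of both arms. That is more than missing detail, because the sampling route is a planned difference between the strategies.

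The direction and size of the distortion cannot be determined from the documents. The 9 to 30 minutes in either direction shown above rests on assumed values for time per draw and net number of draws, and shows only that the omitted part need not be small against 40 minutes per insertion. The point concerns a secondary measure in about 101 patients and leaves the non-inferiority conclusion on day-28 mortality untouched.

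**What to change.** Replace the comparison sentence in section 6.3 with wording such as: *In the 10% microcosting sample, total nurse time and total physician time will each be compared between groups over all tasks in the staff-time criterion: punctures (arterial and venous) for laboratory tests, insertion of an arterial catheter, monitor set-up, and draws from the arterial catheter or another line. The subtotal for arterial puncture, insertion and set-up will be shown as a component.*

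State one time window and use it in sections 2.3, 4.6 and 6.3. It should be a window over which timings were actually recorded in the sampled patients.

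The SAP (Missing analyses and secondary outcomes) lists the number of peripheral venous punctures as not analysable for lack of reliable data. It does not say whether this extends to the timed 10% sample. If it does, say so and label the comparison partial.

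Adding cuff-measurement and dressing time is optional and, if done, should be presented as going beyond the criterion.

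The cost is one sentence plus alignment of the window. Blood sampling is already a timed microcosting step, so no new data collection is called for.
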